Appendix 5 Substudies

Study 1

To undertake a structured feedback process with participating GP practices to determine information relevant to the implementation of hrHPV screening.

To describe perceived and experienced primary care related barriers to the implementation of hrHPV screening incorporating self-testing.

Study 2

To undertake a structured feedback process for a proportion of participants undertaking hrHPV screening.

To describe aspects of the patient reported experience of hrHPV screening, particularly participants undergoing vaginal self-test who have a positive test.

[figure not shown]
Study 3

Assessment of the educational needs and perceived barriers to hrHPV screening among Primary care practitioners undertaking this pilot study.

In addition to collaborative discussion with primary care practices prior to the commencement of related educational activities all health practitioners who will be undertaking screening activities in the practice will be asked to complete a questionnaire that will help inform this process.

By performing a web-based questionnaire prior to commencing education and recruitment for the study.

Appendix 6 Flowchart for management of hrHPV results either clinician taken or vaginal self-test

*Note if a vaginal self-test is taken and the result is positive a cervical cytology specimen is indicated to stratify risk, however in some circumstances it will not change so is

not required. (i.e. HPV16/18 positive) If a cervical test has been taken this will be performed on the same specimen by the laboratory. It is advised that this test is performed within 2 weeks.

**With the new five yearly screening interval, those coming in for their next screening test (after previous cytology screening) any time in the last five years before age 69, i.e. 65 – 69 years of age (inclusive), can exit the programme if their hrHPV test result is negative. This includes those with normal screening histories, with no screening history and those with previous abnormalities who have already been returned to regular interval (three yearly) screening. Exceptions are:

1. Participants who are still in active surveillance following previous abnormalities need to complete their follow-up. So if a test of cure is indicated and hasn't been successfully completed then they need a test of cure – one negative HPV test is not sufficient in this circumstance.
2. Immune deficient participants with a negative hrHPV test need to return in three years for a repeat hrHPV screen, if this falls before 69 years of age
3. Women who have had a recent hysterectomy will need a test of cure if there is high-grade histology in the hysterectomy specimen, which may or may not have been preceded by high-grade cytology.

[figure not shown]
Those who would normally exit the NCSP under the current NCSP exit requirements i.e. have had two normal screening cytology samples between ages 62 and 69 years of age, can exit at 69 years of age without HPV testing (providing not immune deficient or requiring further follow-up because of abnormal results).

***Urgency of referrals to Colposcopy are as follows;

- **Very Urgent** – Suspicion of Malignancy (10 working days)
- **Urgent** – High-grade cytology and/or HPV 16 or 18 positive (20 working days)
- **Semi-Urgent** – other high-risk HPV and low-grade/ASCUS cytology (3 months)
- Colposcopy can be referred as a clinical override e.g. hrHPV other and patient declining cytology triage.

ASCUS: Atypical Squamous Cells of Undetermined Significance hrHPV: high risk human papillomavirus NCSP: National Cervical Screening Programme

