Referral to colposcopy guidelines are in accordance with planned NSU recommendations with the additional safety that patients with low grade cytology and hrHPV other who will be referred to colposcopy.

Referral to colposcopy is indicated for patients with a significant risk of high-grade cervical abnormalities. The recommendations in this pilot study have been agreed with the NCSP and take into consideration the current recommendations for colposcopy referral, risk of CIN2+, colposcopy service capacity, access to colposcopy for underserved populations, and the requirement of data collection from this study in a timely manner to inform implementation of the NCSP. It is important to acknowledge that these recommendations may differ to the final NCSP recommendations and time frames on the basis of this and other information yet to be determined.

Patients with hrHPV other and low-grade cytology are referred to colposcopy in this study because the burden of disease in this group is not documented in NZ. Within this study we are unable to follow up this group via repeated testing, in addition patients over 30 with low grade cytology and hrHPV are currently referred to colposcopy and laboratories are obliged to put this advice on their cytology reports. It is anticipated in the new program that these patients will undergo repeat testing at 12 and 24 months as per the Australian program.

Risk of CIN2+ can be stratified as below:

Low risk

- Other HPV positive, cytology normal or unknown

Intermediate risk

- HPV 16/18 positive with normal cytology
- Other HPV with ASCUS/low grade cytology (the risk for this group in NZ is unknown and may be low)

High risk

- HPV 16/18 positive with ASCUS/low grade/high-grade/AGC cytology
- Other HPV with high-grade/AGC cytology

Patients stratified as low risk will be recommended to have a repeat screen in 12 months.

Patients with intermediate risk will be referred to colposcopy as a semi urgent referral (for the purpose of the study we request these patients are seen within 3 months).

Patients with HPV 16/18 who do not undergo cytology may be referred as high risk because their risk is undetermined and may be high risk.

Patients with high risk of CIN2+ are referred for colposcopy (20 working days).

Patients with suspected cancer will be seen within 10 working days and treated accordingly as per regional practice.

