In participants that had a cytology test prior to colposcopy, the number (and percentage) informed of their cytology results by:

- Face to face appointment with a staff member at their GP clinic
- Phone call with a staff member from their GP clinic
- Text
- Other form of contact.

Data to be presented separately for participants negative for hrHPV, participants positive for HPV16 and/or 18, and participants positive for hrHPV other than 16 or 18.

COLPOSCOPY

The mean, median and range for the time between an hrHPV test report being issued and GP referral for colposcopy.

Data to be presented separately by whether participants had a cervical or vaginal hrHPV test.

Data to also be presented separately for participants negative for hrHPV, participants positive for HPV16 and/or 18, and participants positive for hrHPV other than 16 or 18.

HPV-based Screening Implementation Study Protocol

In participants that had a cytology test prior to their colposcopy referral, the mean, median and range for the time between the cytology result report being issued and referral for colposcopy.

Data to be presented separately for participants negative for hrHPV, participants positive for HPV16 and/or 18, and participants positive for hrHPV other than 16 or 18.

The number (and percentage) of participants that had a referral for colposcopy by classification of urgency.

Data to be presented separately for participants negative for hrHPV, participants positive for HPV16 and/or 18, and participants positive for hrHPV other than 16 or 18.

In participants referred for colposcopy, the number (and percentage) that received 1, 2, 3 or >3 invitations for an appointment.

Data to be presented separately for participants negative for hrHPV, participants positive for HPV16 and/or 18, and participants positive for hrHPV other than 16 or 18.

In participants that had a colposcopy, the mean, median and range for time from GP referral to their colposcopy appointment.

Data to be presented separately for each classification of urgency.

Data to also be presented separately for participants negative for hrHPV, participants positive for HPV16 and/or 18, and participants positive for hrHPV other than 16 or 18.

In participants that had a cytology test during colposcopy, the number (and percentage) with a result of:

- Negative for dysplasia or malignancy
- ASC-US (atypical squamous cells of undetermined significance - excluding ASC-US possible high grade)

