In order to align with current NCSP practices, in terms of database requirements and automatic recall procedures, all patients in the clinician-taken sample group will have a cytology assessment of the sample they have already given, thus, do not need to return for a follow up cervical screen. The two groups, therefore, cannot be directly compared in terms of failure to return for follow up. In addition, as the clinician-taken and self-sample groups are self-selected they will be different and, hence, outcomes from the two groups will be recorded but cannot be directly compared.

Due to the relatively small size of this study and the unlikely outcome of a high-grade cervical abnormality, outcomes related to colposcopy referral will lack the power for stratification. However, the choice of screening method may usefully be able to be stratified.

Transfer of data and patient care to the NCSP.

The NCSPR will be informed of all patients participating in the study.

As the NCSPR is not currently able to manage the results of hrHPV screening this information will be overseen by the study team. The study team will act in place of the NCSPR to provide reminders to the practices when patients are overdue further investigations or repeat testing and to ensure management recommendations are correct. Following colposcopy or on completion of the study when the NCSPR is able to manage these patients' information they will be referred back to the NCSPR

Results of all cytology tests and hrHPV tests and colposcopy records will automatically be referred to the NCSPR. The study team will follow all patients to the end of the study to ensure patients who require colposcopy have been seen.

At completion of the study enrolled patients will fall under the following categories.

- Normal screen, next routine screen to be performed at the normal screening interval (5 years)
- Normal screen but because of previous abnormality follow up recommended in 12 months
- Abnormal screen referred to colposcopy attended follow up dictated by colposcopist and referred back to NCSP

- Abnormal screen colposcopy recommended lost to follow up/colposcopy declined
- Abnormal screen follow-up cytology advised but declined/lost to follow up
- Abnormal screen cytology performed follow up in 12 months recommended

This information will be shared with the NCSP (as far as possible in a manner that is suitable to the NCSP) and patients will be discharged to GP practice and NCSP

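### HPV 16/18 with normal cytology is semi-urgent (3 months) in the referral section but urgent (20 working days) in the Appendix 6 legend

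*Protocol*

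**What the plan says.** The main-text section Referral to colposcopy stratifies patients by risk of CIN2+. Its intermediate group includes "HPV 16/18 positive with normal cytology". It then states: "Patients with intermediate risk will be referred to colposcopy as a semi urgent referral", adding that "for the purpose of the study we request these patients are seen within 3 months". The same section reserves the high-risk class, with its 20-working-day target, for HPV 16/18 with ASCUS or worse cytology and for other hrHPV with high-grade or glandular cytology. It makes one allowance: "Patients with HPV 16/18 who do not undergo cytology may be referred as high risk".

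The legend to the Appendix 6 flowchart defines the urgent class as "High-grade cytology and/or HPV 16 or 18 positive (20 working days". Its semi-urgent class contains only "other high-risk HPV and low-grade/ASCUS cytology (3 months".

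The colposcopy part of Outcome measures reports the number referred by urgency class, and the time from referral to the colposcopy appointment with this instruction: "Data to be presented separately for each classification of urgency".

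**The concern.** Both texts are current, and they give the same patient different instructions. In the legend, the and/or makes an HPV 16 or 18 result sufficient for the urgent class. In the main text, a normal cytology result moves that patient to semi-urgent. A patient seen at 8 weeks is on time under one rule and late under the other.

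Within the HPV 16/18 group, two outcomes depend on the choice: the split of referrals by urgency, and the referral-to-colposcopy times by urgency class. If practices follow different texts, each class mixes two definitions. The database reminders and the check of recommendations against guidelines, described in Appendix 2 under Quality assurance, may also be affected, because they need a single time frame for each patient.

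Appendix 3 gives a CIN2+ risk of 24% for HPV 16 with normal cytology, so the target time for this group has some clinical weight.

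**Working it through.** **The two rules side by side**

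| HPV 16/18 positive, by cytology | Referral to colposcopy | Appendix 6 legend |
|---|---|---|
| ASCUS or worse | High risk, 20 working days | Urgent, 20 working days |
| Normal | Intermediate, semi-urgent, 3 months | Urgent, 20 working days |
| Not done | May be referred as high risk | Urgent, 20 working days |

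The conflict lies in the middle row. In the bottom row the texts can agree. Taking 20 working days as 4 weeks and 3 months as about 13 weeks, the targets differ by about 9 weeks.

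**Does anything reconcile them?** The allowance for missing cytology does not cover a normal result. The clinical override in Referral to colposcopy is discretionary and names other triggers (appearance of the cervix, symptoms, under-screening, perceived barriers). The instruction under Informing patients to refer HPV 16/18 promptly sets no urgency class. Appendix 4 counts urgent referrals under both policies and chooses neither.

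**The protocol's own figures (Appendix 4).** Inputs: 7% hrHPV positive (range 5–10%), 25% of positives HPV 16/18, 30% of those with normal cytology.

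- HPV 16/18 positive per 1000 screened: 1000 × 0.07 × 0.25 = 17.5 (stated 18).
- Of these, normal cytology: 17.5 × 0.30 = 5.25.
- Urgent referrals if this group is semi-urgent: 26 − 5.25 = 20.75 (stated 21).

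The stated 26 and 21 per 1000 therefore differ by exactly the group in dispute.

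**Patients affected among 3000, if every HPV 16/18 positive patient has cytology**

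- At 7%: 3000 × 0.07 × 0.25 × 0.30 = 15.8.
- At 5%: 11.3. At 10%: 22.5.
- If the 12% that Statistical Considerations assumes for self-tests applied to everyone: 27.

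**Patients affected if only clinician-taken samples have cytology.** Statistical Considerations expects 900–1200 such participants and says "all patients in the clinician-taken sample group will have a cytology assessment of the sample they have already given". Cytology after a self-test is recommended but not required for HPV 16/18.

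- At 7%: 900 × 0.07 × 0.25 × 0.30 = 4.7, and 1200 × 0.07 × 0.25 × 0.30 = 6.3.
- Over 5–10%: 3.4 (900 at 5%) to 9.0 (1200 at 10%).

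**Urgent share of the HPV 16/18 group at 7%.** The group is 3000 × 0.07 × 0.25 = 52.5.

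- Legend: 100%.
- Main text, all with cytology: 1 − 15.75/52.5 = 70%.
- Main text, cytology on clinician-taken samples only and the rest referred as high risk: 1 − 6.3/52.5 = 88% to 1 − 4.7/52.5 = 91%.

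**The case against.** The best defence is that this is a drafting slip with little effect. The limits are nested: a patient seen within 20 working days satisfies both texts, so nobody receives an unsafe or impossible instruction. The adverse-event reporting in Appendix 2 uses a 3-month limit for colposcopy attendance under either rule. The study is descriptive, and Statistical Considerations already says that colposcopy outcomes lack power for stratification. Appendix 2 does not state that the reminders or the guideline check use urgency class, and the Data Management Plan is a separate document. The version history suggests that the legend's urgency criteria were added on 1 March 2023, shortly before the last date for agreeing to take part, so many referrals may have been made without them. The flowchart itself is not visible and may treat normal cytology separately.

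Most of this stands as a limit on size. The link to the reminders is partly inferred, and the timing argument, itself an inference, would lower the number exposed. None of it removes the contradiction. Nested limits do not tell the analyst which class a patient belongs to, and the outcomes are reported by class. Nor do they tell a clinic whether a visit at 8 weeks is late. Low power for stratification is no reason to leave a reported category with two definitions.

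**Conclusion.** The contradiction holds as written and should be corrected. Its effect is limited: about 16 of 3000 participants at 7% positivity if all HPV 16/18 positive patients have cytology (11 to 23 over 5–10%), or about 5 to 6 if only clinician-taken samples do (3 to 9). The urgent share of the HPV 16/18 group is 100% under the legend and between 70% and 91% under the main text.

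These figures rest on the protocol's planning rates, which it describes as estimates with little New Zealand data behind them. The 88–91% also assumes that HPV 16/18 patients without cytology are referred as high risk, which the protocol permits but does not require.

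Results for other hrHPV, total referrals, CIN2+ yield and the reporting of non-attendance at 3 months are unaffected. The nominal class can be rebuilt from recorded HPV and cytology results, but the scheduling a patient received cannot be changed afterwards. The conclusion rests on the legend and the main text, because the flowchart figure could not be seen.

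**What to change.** Agree one class with the NCSP for HPV 16/18 with normal cytology and state it identically in both places. Either add the group to the semi-urgent line of the Appendix 6 legend, or move it into the 20-working-day group in Referral to colposcopy. Which class is clinically right is for the study team and the NCSP to decide.

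Check that the database reminders and the guideline cross-check use the agreed class. For referrals already made, derive the class from the recorded HPV and cytology results, and report the urgency actually assigned alongside it.

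The cost is a one-line amendment in one of the two places, a short memo to sites and a check of the reminder rule.

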Appendix 7 Flowchart recommendations for colposcopy management

hrHPV: high risk human papillomavirus MDM: Multidisciplinary Meeting
